8.4.5 Pregnancy testing

All pre-menopausal women who are not surgically sterile will have a serum pregnancy testing at the screening visit and urine pregnancy testing at other study visits, the time points refer to [Table 1-2](#).

Additional pregnancy testing might be performed if requested by local requirements.

As per [Section 4.5](#), during a public health emergency as declared by local authorities' i.e. pandemic, epidemic or natural disaster, that limits or prevents on-site study visits, if participants cannot visit the site to have serum pregnancy tests, urine pregnancy test kits may be used. Relevant participants can perform the urine pregnancy test at home and report the result to the site. A communication process should be established with the participant so that the site is informed and can verify the pregnancy test results (e.g. following country specific measures).

Assessments of fertility

A woman is considered of childbearing potential from menarche and until becoming post menopausal unless permanently sterile. Permanent sterilization methods include hysterectomy, bilateral salpingectomy and bilateral oophorectomy. Medical documentation of oophorectomy, hysterectomy, or tubal ligation must be retained as source documents.

A postmenopausal state is defined as no menses for 12 months without an alternative medical cause and an appropriate clinical profile.

In absence of the medical documentation confirming permanent sterilization, or if the post-menopausal status is not clear, the investigator should use his medical judgment to appropriately evaluate the fertility state of the woman and document it in the source document. In such cases,

FSH testing is required of any female participant regardless of reported reproductive/menopausal status at screening visit.

8.4.6 Appropriateness of safety measurements

The safety assessments selected are standard for this indication/participant population.

8.5 Additional assessments

No additional tests will be performed on participants entered into this study.

8.6 Adverse events (AEs), serious adverse events (SAEs), and other safety reporting

The definitions of adverse events (AEs) and serious adverse events (SAEs) can be found in [Section 8.6.1](#) and [Section 8.6.2](#).

AEs will be reported by the participant (or, when appropriate, by a caregiver, surrogate, or the participant's legally authorized representative).

The Investigator and any qualified designees are responsible for detecting, documenting, and recording events that meet the definition of an AE or SAE and remain responsible for following up (see [Section 7](#)).

The method of recording, evaluating, and assessing causality of AEs and SAEs and the procedures for completing and transmitting SAE reports are provided in [Section 8.6.3](#).

8.6.1 Adverse events

An adverse event (AE) is any untoward medical occurrence (e.g. any unfavorable and unintended sign [including abnormal laboratory findings], symptom or disease) in a clinical investigation participant after providing written informed consent for participation in the study. Therefore, an AE may or may not be temporally or causally associated with the use of a medicinal (investigational) product.

The Investigator has the responsibility for managing the safety of individual participant and identifying adverse events. Novartis qualified medical personnel will be readily available to advise on trial-related medical questions or problems.

The occurrence of adverse events must be sought by non-directive questioning of the participant at each visit during the study. Adverse events also may be detected when they are volunteered by the participant during or between visits or through physical examination findings, laboratory test findings, or other assessments

Adverse events must be recorded under the signs, symptoms, or diagnosis associated with them, accompanied by the following information (as far as possible) (if the event is serious refer to [Section 8.6.2](#)):

1. The severity grade:

- mild: usually transient in nature and generally not interfering with normal activities
- moderate: sufficiently discomforting to interfere with normal activities
- severe: prevents normal activities

2. Its relationship to the study treatment. If the event is due to lack of efficacy or progression of underlying illness (i.e. progression of the study indication) the assessment of causality will usually be 'Not suspected.' The rationale for this guidance is that the symptoms of a lack of efficacy or progression of underlying illness are not caused by the trial drug, they happen in spite of its administration and/or both lack of efficacy and progression of underlying disease can only be evaluated meaningfully by an analysis of cohorts, not on a single participant
3. Its duration (start and end dates or ongoing) and the outcome must be reported
4. Whether it constitutes a SAE (see [Section 8.6.2](#) for definition of SAE) and which seriousness criteria have been met
5. Action taken regarding with study treatment.

All adverse events must be treated appropriately. Treatment may include one or more of the following:

- Dose not changed
- Dose Reduced/increased
- Drug interrupted/permanently discontinued

6. Its outcome (i.e. recovery status or whether it was fatal)

Conditions that were already present at the time of informed consent should be recorded in medical history of the participant.

Adverse events (including lab abnormalities that constitute AEs) should be described using a diagnosis whenever possible, rather than individual underlying signs and symptoms.

Adverse event monitoring should be continued for at least 30 days following the last study treatment visit.

Once an adverse event is detected, it must be followed until its resolution or until it is judged to be not recovered/not resolved (e.g. continuing at the end of the study), and assessment must be made at each visit (or more frequently, if necessary) of any changes in severity, the suspected relationship to the interventions required to treat it, and the outcome.

Information about adverse drug reactions for the investigational drug can be found in the Investigator's Brochure (IB).

Abnormal laboratory values or test results constitute adverse events only if they fulfill at least one of the following criteria:

- they induce clinical signs or symptoms
- they are considered clinically significant
- they require therapy

Clinically significant abnormal laboratory values or test results must be identified through a review of values outside of normal ranges/clinically notable ranges, significant changes from baseline or the previous visit, or values which are considered to be non-typical in participant with the underlying disease. Alert ranges for laboratory and other test abnormalities are included in [Section 10.3](#).

8.6.2 Serious adverse events

An SAE is defined as any adverse event [appearance of (or worsening of any pre-existing)] undesirable sign(s), symptom(s), or medical conditions(s) which meets any one of the following criteria:

- fatal
- life-threatening

Life-threatening in the context of a SAE refers to a reaction in which the participant was at risk of death at the time of the reaction; it does not refer to a reaction that hypothetically might have caused death if it were more severe (please refer to the International Council for Harmonization of Technical Requirements for Pharmaceuticals for Human Use (ICH)-E2D Guidelines).

- results in persistent or significant disability/incapacity
- constitutes a congenital anomaly/birth defect, fetal death
- requires inpatient hospitalization or prolongation of existing hospitalization, unless hospitalization is for:
 - routine treatment or monitoring of the studied indication, not associated with any deterioration in condition (primary hypercholesterolemia)
 - elective or pre-planned treatment for a pre-existing condition that is unrelated to the indication under study and has not worsened since signing the informed consent
 - social reasons and respite care in the absence of any deterioration in the participant's general condition
 - treatment on an emergency outpatient basis for an event not fulfilling any of the definitions of a SAE given above and not resulting in hospital admission
- is medically significant, e.g. defined as an event that jeopardizes the participant or may require medical or surgical intervention to prevent one of the outcomes listed above

Medical and scientific judgment should be exercised in deciding whether other situations should be considered serious reactions, such as important medical events that might not be immediately life-threatening or result in death or hospitalization but might jeopardize the participant or might require intervention to prevent one of the other outcomes listed above. Such events should be considered as "medically significant." Examples of such events are intensive treatment in an emergency room or at home for allergic bronchospasm, blood dyscrasias, or convulsions that do not result in hospitalization or development of dependency or abuse (please refer to the ICH-E2D Guidelines).

All new malignant neoplasms will be assessed as serious under "medically significant" if other seriousness criteria are not met and the malignant neoplasm is not a disease progression of the study indication.

All reports of intentional misuse and abuse of the product are also considered serious adverse events irrespective of whether a clinical event has occurred.

Any suspected transmission via a medicinal product of an infectious agent is also considered a serious adverse reaction.

If an SAE occurs, investigators is encouraged to take any appropriate actions immediately based on their judgments and relevant clinical guidance.

8.6.3 SAE reporting

To ensure participant safety, every SAE, regardless of causality, occurring after the participant has provided informed consent and until 30 days after the last study visit (or 90 days after the last administration of study drug, whichever is longer) must be reported to Novartis safety immediately, without undue delay, but under no circumstances later than within 24 hours of obtaining knowledge of the events (Note: If more stringent, local regulations regarding reporting timelines prevail). Detailed instructions regarding the submission process and requirements are to be found in the Investigator folder provided to each site. Information about all SAEs is collected and recorded on the eSAE with paper backup Serious Adverse Event Report Form; all applicable sections of the form must be completed in order to provide a clinically thorough report.

Consider the following 2 categories to determine SAE reporting timeframes:

1. Screen Failures (e.g. a participant who is screened but is not treated or randomized): SAEs occurring after the participant has provided informed consent until the time the participant is deemed a Screen Failure must be reported to Novartis.
2. Randomized OR Treated Participants: SAEs collected between time participant signs ICF until 30 days after the last study visit (or 90 days after the last administration of study drug, whichever is longer)

All follow-up information for the SAE including information on complications, progression of the initial SAE and recurrent episodes must be reported as follow-up to the original episode immediately, without undue delay, but under no circumstances later than within 24 hours of the Investigator receiving the follow-up information (Note: If more stringent, local regulations regarding reporting timelines prevail). An SAE occurring at a different time interval or otherwise considered completely unrelated to a previously reported one must be reported separately as a new event.

If the SAE is not previously documented in the Investigator's Brochure or Package Insert (new occurrence) and is thought to be related to the study treatment, a Chief Medical Office and Patient Safety (CMO&PS) Department associate may urgently require further information from the Investigator for health authority reporting. Novartis may need to issue an Investigator Notification (IN) to inform all Investigators involved in any study with the same study treatment that this SAE has been reported.

Suspected Unexpected Serious Adverse Reactions (SUSARs) will be collected and reported to the competent authorities and relevant ethics committees in accordance with Novartis procedures and applicable global regulations or as per national regulatory requirements in participating countries.

Any SAEs experienced after the 30-day period following the last study visit (or 90 days after the last administration of study drug, whichever is longer) should only be reported to Novartis Safety if the Investigator suspects a causal relationship to study treatment, unless otherwise specified by local law/regulations.

8.6.4 Pregnancy

If a female trial participant becomes pregnant, the study treatment should be stopped, and the pregnancy consent form should be presented to the trial participant. The participant must be given adequate time to read, review and sign the pregnancy consent form. This consent form is necessary to allow the Investigator to collect and report information regarding the pregnancy. To ensure participant safety, each pregnancy occurring after signing the informed consent must be reported to Novartis within 24 hours of learning of its occurrence. The pregnancy should be followed up to determine outcome, including spontaneous or voluntary termination, details of the birth, and the presence or absence of any birth defects, congenital abnormalities, or maternal and/or newborn complications.

Pregnancy should be recorded and reported by the Investigator to the Novartis Chief Medical Office and Patient Safety (CMO&PS). Pregnancy follow-up should be recorded on the same form and should include an assessment of the possible relationship to the study treatment any pregnancy outcome. Any SAE experienced during pregnancy must be reported.

After consent is provided, the pregnancy reporting will occur up to one year after the estimated date of delivery.

8.6.5 Disease-related events and/or disease-related outcomes not qualifying as AEs or SAEs

Not Applicable.

8.6.6 Adverse events of special interest

Not Applicable.

8.7 Pharmacokinetics

PK parameters are not evaluated in this study.

[REDACTED]

[REDACTED]

[REDACTED]

[REDACTED]

[REDACTED]

[REDACTED]

8.9 Immunogenicity assessments

Immunogenicity is not evaluated in this study.

8.10 Health economics OR Medical resource utilization and health economics

Not Applicable.

9 Statistical considerations

The primary analyses will be conducted after the database lock for the core part, when all randomized participants have completed the visit at Day 180 (or have discontinued from the study before EOC). The final analyses will be conducted when the trial ended.

Details of the statistical analysis and data reporting will be summarized in the statistical analysis (SAP) document finalized before database lock.

Any data analysis carried out independently by the investigator should be submitted to Novartis before publication or presentation.

9.1 Analysis sets

The following analysis sets will be used for statistical analyses:

The screened set (SCR) consists of all participants who signed the informed consent. The SCR includes only unique screened participants, i.e., in the case of re-screened participants only the chronologically last screening data is counted.

The Randomized Analysis Set (RAS) consists of all participants who received a randomization number, regardless of receiving trial medication.

The Full Analysis Set (FAS) consists of all randomized participants with the exception of those participants who have not been qualified for randomization and have not received study drug, but have been inadvertently randomized into the study. Following the intent-to-treat (ITT) principle, participants will be analyzed according to the treatment they have been assigned to at randomization.

The Safety Analysis Set (SAF) includes all participants who received at least one dose of study drug. Participants will be analyzed according to the study treatment actually received.

Note: The last part of the definition of the FAS is what is often referred to as mis-randomized participants i.e. participants for whom IRT calls were made by the site either prematurely or inappropriately prior to confirmation of the participant's final randomization eligibility and double-blind medication was not administered to the participant. These participants would subsequently not continue to take part in the study or be followed-up. Mis-randomized participants will not be included in the FAS, but they will be included in the RAS. Further

exclusions from the FAS may only be justified in exceptional circumstances (e.g., serious Good Clinical Practice (GCP) violations).

9.2 Statistical analyses

Details of the statistical analysis and data reporting will be summarized in the Statistical Analysis Plan (SAP) document finalized before the database lock.

9.2.1 General considerations

Efficacy variables will be analyzed based on the FAS. The SAF will be used for the analyses of safety variables.

9.2.2 Participant demographics and other baseline characteristics

Demographic and other baseline data will be summarized descriptively by treatment group for the FAS. Categorical data will be presented as frequencies and percentages by treatment group. For continuous data, number of non-missing observations, mean, standard deviation, median, minimum, and maximum will be presented by treatment group. For selected parameters, 25th and 75th percentiles will also be presented by treatment group.

Relevant medical histories will be summarized by system organ class and preferred term, separately by treatment group.

9.2.3 Treatments

The SAF will be used for the analyses in this section.

Study treatment

The number and percentage of participants receiving study dose at each dosing visit will be summarized by treatment group. The number of doses received during the core part (excluding Day 180 dose) and during the extension part (including Day 180 dose) will also be summarized by treatment group.

Prior and concomitant therapies

Prior or concomitant medications will be summarized for the SAF in separate tabulations based on the coding dictionary used. Medications will be presented in alphabetical order, by Anatomical Therapeutic Chemical (ATC) class and preferred terms. Tables will show the overall number and percent of participants receiving at least one drug of a particular ATC class and at least one drug in a particular preferred term.

Prior medications and significant non-drug therapies will be summarized by treatment group. Concomitant medications and significant non-drug therapies prior to and after the start of the study treatment will be summarized by treatment group and by part.

9.3 Primary endpoint(s)/estimand(s) analysis

The primary aim of the study is to demonstrate the superiority of inclisiran as monotherapy, compared to placebo, in reducing LDL-C.

The FAS will be used for the primary efficacy analysis.

9.3.1 Definition of primary endpoint(s)

The primary endpoint of the study is the percentage change from baseline at Day 150 in LDL-C.

9.3.2 Statistical model, hypothesis, and method of analysis

The primary objective is to demonstrate the superiority of inclisiran as monotherapy, compared to placebo, in reducing LDL-C as measured by percentage change from baseline at Day 150. The justification of the corresponding primary estimand is detailed in [Section 3.1](#).

The primary statistical hypothesis is stated as below.

- H_0 : the mean difference (inclisiran minus placebo) in percentage change from baseline at Day 150 in LDL-C is no less than zero.
- H_1 : the mean difference (inclisiran minus placebo) in percentage change from baseline at Day 150 in LDL-C is less than zero.

The study can be claimed a success if the null hypothesis (H_0) is rejected at the one-sided significance level of 0.025.

The primary efficacy endpoint will be analyzed using an Analysis of Covariance (ANCOVA) model, in which the response variable will be the percentage change from baseline at Day 150 in LDL-C, treatment will be included as fixed-effect factor and baseline LDL-C will be included as a covariate.

Based on the ANCOVA model, the estimate and the 95% confidence interval will be provided for the adjusted mean difference between inclisiran and placebo, and for the adjusted mean for both inclisiran and placebo groups. The one-sided p-value will be provided for the primary null hypothesis.

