- The overall study duration is approximately 374 days but can vary depending on individual screening and the visit window.
- Participants will receive inclisiran/placebo subcutaneous injections on Day 1, Day 90, Day 180. And all participants will receive inclisiran treatment on Day 270.
- Visits will be on Day 1, Day 30, Day 90, Day 150 (primary endpoint), Day 180 (end of core part, EOC), Day 210, Day 270, Day 330 and Day 360 (EOS).

Treatment of interest

For primary estimand, the treatment of interest is inclisiran sodium 300 mg s.c. at Day 1 and Day 90 as monotherapy (no other lipid lowering therapy) comparing to matching placebo s.c. at Day 1 and Day 90 as monotherapy, regardless of study treatment discontinuation.

Number of Participants:

Approximately 200 participants will be randomized 1:1 to inclisiran and placebo .

Key Inclusion criteria

- Written informed consent must be obtained before any assessment is performed
- Adults ≥ 18 and ≤ 75 years of age
- Fasting LDL-C value of ≥ 130 mg/dL but <190 mg/dL at screening
- Triglycerides ≤ 400 mg/dL at screening

- Categorized as low or moderate ASCVD risk by the 2016 Chinese guideline for the management of dyslipidemia in adults at screening
- No plan of introducing other lipid lowering therapy during the study participation

Key Exclusion criteria

- Use of any lipid-lowering therapy within 90 days prior to screening visit
- Previous exposure to inclisiran or any non-mAb PCSK9-targeted therapy, either as an investigational or marketed drug within 2 years prior to screening visit
- History of ASCVD
- Diabetes mellitus or fasting plasma glucose at screening \geq 7.0 mmol/L or glycated hemoglobin (hemoglobin A1c) (HbA1c) \geq 6.5%
- Active liver disease defined as any known current infectious, neoplastic, or metabolic pathology of the liver or unexplained elevations in alanine aminotransferase (ALT), aspartate aminotransferase (AST), >3 x the upper limit of normal (ULN), or total bilirubin >2 x ULN at screening
- Estimated glomerular filtration rate (eGFR) $<$ 30 mL/min/1.73m² at screening

Treatment Groups:

At Day 1 (Baseline), all participants will be randomized 1:1 to one of the two treatment groups:

- **Inclisiran Group:** 100 participants. Treated with inclisiran sodium 300mg s.c. on Day 1, Day 90 and Day 270, and with matching placebo s.c. on Day 180.

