9.4.1.1 Efficacy and/or pharmacodynamic endpoints for core part

The secondary efficacy endpoints for core part are listed as follows:

- Absolute change in LDL-C from baseline at Day 150
- Percentage and absolute change in PCSK9, TC, HDL-C, non-HDL-C, ApoB, ApoA-1, Lp(a) and TG from baseline at Day 150

All secondary efficacy endpoints for core part will be analyzed using the same ANCOVA model as for the primary efficacy endpoint. Lipoprotein (a) will be log-transformed before modeling. The model will include treatment as fixed effect, and baseline value as a covariate. The adjusted mean difference between inclisiran and placebo and corresponding two-sided 95% CIs will be provided separately.

Details of the analyses for secondary efficacy endpoints for core part and sensitivity analyses if necessary will be specified in the SAP.

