9.9 Sample size determination

9.9.1 Primary endpoint(s)

This study is designed to randomize approximately 200 Participants (with randomization ratio of 1:1 to inclisiran and placebo arms) in order to provide adequate information to characterize the safety profile of inclisiran as well as to have sufficient power for the primary efficacy endpoint.

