2. Participants randomized to Inclisiran Group will be treated with inclisiran sodium 300mg s.c. on Day 1 and Day 90 and Day 270, and with matching placebo s.c. on Day 180. Participants randomized to Control Group will be treated with matching placebo s.c. on Day 1 and Day 90, and with inclisiran sodium 300mg on Day 180 and Day 270.
3. The end of core part visit. The database lock for the core part is planned to occur after all randomized participants have completed the EOC visit (or have discontinued from the study before EOC). The primary endpoint analysis will be conducted after the database lock for the core part.
4. Participants who discontinue from study should be scheduled for an Early Exit visit if they agree. This Early Exit visit is suggested to be scheduled at least 30 days after last injection. If not possible, to set an Early Exit visit as soon as possible is also acceptable.

On Day 1 (Baseline), approximately 200 eligible participants who meet all inclusion and not meet any exclusion criteria will be randomized 1:1 to Inclisiran Group and Control Group. Study visits of core part will occur on Day 1 (baseline visit), Day 30, Day 90, Day 150, and Day 180. On Day 1 and Day 90 visits, inclisiran s.c. or placebo s.c. will be administered at the site by a healthcare professional. The primary endpoint will be assessed at Day 150. The EOC visit will be conducted on Day 180.

The extension part starts with a dose on Day 180 after all core part assessments are completed. In order to maintain the blind for the treatment group assignment, participants randomized to Control Group will receive inclisiran, while participants randomized to Inclisiran Group will receive placebo on Day 180. All participants will then receive inclisiran sodium 300 mg on Day 270, which will be the third dose of inclisiran for Inclisiran Group, and the second dose of inclisiran for Control Group. All injections will be administered at the site by a healthcare professional. The EOS visit (Day 360) will be the last visit of the study.

The randomization will not be stratified.

The core part analyses will be conducted when all randomized participants have completed the visit at Day 180 (or have discontinued from the study). The final analyses will be conducted when the trial ended. No interim analyses are planned.

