#### **2.5.6 Supplementary analyses**

A plot displaying descriptive mean percentage change in LDL-C from baseline up to Day 180 visit for both treatment groups will be provided, using the observed data.

Subgroup analyses to assess the homogeneity of the treatment effect across demographic and baseline characteristics will be performed in subgroups as specified in [Section 2.2.1](#). The subgroup analyses will use the same ANCOVA model as specified above. The difference in the adjusted means between treatment groups, corresponding two-sided 95% CI and one-sided p-value will also be provided for each of the subgroups. The adjusted means in both treatment groups, corresponding two-sided 95% CI will also be provided for each of the subgroups. The subgroup analysis results will be left blank if the subgroup analysis model did not converge. Forest plot will be provided for subgroup analyses. The multiply imputed datasets created from primary analysis will be used in the subgroup analyses. The results from the subgroup analysis models will be combined using the Rubin's rule.

Two sets of supplementary analyses under different estimand will also be conducted.

For the first one, all three intercurrent events, including discontinuation of study treatment, use of prohibited LLT under certain conditions and death due to CV or non-CV causes, will be handled with a hypothetical strategy. Data after all these intercurrent events will be multiply imputed under missing at random assumption. Missing values not related to intercurrent events will also be multiply imputed under missing at random assumption. Details are specified in [Appendix 5.4.1.2](#).

For the second one, the intercurrent events of discontinuation of study treatment and death due to CV or non-CV causes will be handled in the same way as in the primary analysis. Use of prohibited LLT under certain conditions will be treated with a treatment policy strategy, keeping treatment labels as assigned at randomization. Retrieved drop out (RDO) data collected after use of prohibited LLT under certain conditions will be used for the analysis. Missing data after usage of prohibited LLT will be multiply imputed using a control-based PMM. Missing values not related to intercurrent events will also be multiply imputed using a control-based PMM. Details are specified in [Appendix 5.4.1.3](#).

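### The ANCOVA pools one residual variance across arms, so the 95% CIs for each arm's adjusted mean miss nominal coverage if inclisiran changes the spread of percentage change; the primary comparison is not affected

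*Protocol*

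**What the plan says.** Protocol 9.3.2 defines the primary model: "treatment will be included as fixed-effect factor and baseline LDL-C will be included as a covariate". From it come 95% intervals "for the adjusted mean difference between inclisiran and placebo, and for the adjusted mean for both inclisiran and placebo groups", and the null hypothesis must be "rejected at the one-sided significance level of 0.025". SAP 2.5.2 repeats the model and these outputs.

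The model is then reused:

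- Protocol 9.4.1.1: "All secondary efficacy endpoints for core part will be analyzed using the same ANCOVA model as for the primary efficacy endpoint". Protocol 9.4.1.1 and SAP 2.6.1.1 promise an interval for the difference only.
- SAP 2.5.6 fits it in each subgroup, with an interval and one-sided p-value for the difference, a forest plot, and arm-level intervals: "The adjusted means in both treatment groups, corresponding two-sided 95% CI will also be provided for each of the subgroups". SAP 2.6.6 does the same, with two-sided p-values, for absolute change in LDL-C and for percentage change in PCSK9, TC, non-HDL-C and ApoB.
- SAP 5.4.1.1 runs it in each of 100 imputed datasets and combines the results by Rubin's method.

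Neither document mentions a variance by arm, robust standard errors, or Satterthwaite or similar degrees of freedom. On allocation, protocol 1.1 says "Approximately 200 participants will be randomized 1:1 to inclisiran and placebo" and SAP 1.1 says "The randomization will not be stratified".

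**The concern.** An ANCOVA specified without qualification has a single residual variance, estimated from both arms. The standard error of each arm's adjusted mean is built from that pooled value, whichever arm it describes. Pooling is inferred from the model as written; neither document says it outright.

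There are two reasons to expect unequal spread. First, percentage change is multiplicative. Protocol 2.2 cites a placebo-adjusted LDL-C change of -57.2% in the earlier Asian phase 3 study. A reduction of that order shrinks within-person noise on the percentage scale, while variation between people in response adds spread. These pull in opposite directions and would have to cancel to leave equal SDs. Second, if retrieved-dropout data are judged insufficient, SAP 2.5.3 and 5.4.1.1 impute missing post-discontinuation values in the inclisiran arm from control-arm data, which can widen that arm only.

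What is at stake is the accuracy of the arm-level LDL-C reductions reported with their intervals, overall and by subgroup. Rubin's rules do not repair this: they add between-imputation variance to within-imputation variances that are already miscalibrated.

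**Working it through.** **Inputs.** From the documents: about 200 participants, 1:1, so 100 per arm; the ANCOVA above; nominal 95%. Assumed, because the documents give no SD: inclisiran/placebo SDs of percentage change of 17/14, 21/13 and 12/17 for LDL-C, and 12/33 as a wide case for PCSK9. Subgroup sizes are also assumed.

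**The plan's own figure.** Protocol 9.9.1 states N with the aim "as well as to have sufficient power for the primary efficacy endpoint", but gives no SD, effect size or power, so 200 cannot be reproduced. Under assumed effects of 20 to 57.2 points and SDs of 15 to 40, power at 100 per arm is 94.2% or more. Power is not the issue here.

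**Formulas (large sample).**

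- Pooled SD: sp = sqrt{[(n1-1)s1² + (n0-1)s0²]/(n1+n0-2)}
- SE ratio for an arm mean: r = sp/s of that arm
- SE ratio for the difference: r = sp·sqrt(1/n1+1/n0) / sqrt(s1²/n1+s0²/n0)
- Coverage = 2Φ(1.96·r) - 1

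**Arm means, 100 v 100.** For 17/14, sp = sqrt[(289+196)/2] = 15.57. The inclisiran ratio is 15.57/17 = 0.916 and the placebo ratio is 15.57/14 = 1.112.

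| SD incl/pbo | sp | Inclisiran mean | Placebo mean | Difference |
|---|---|---|---|---|
| 17/14 | 15.57 | 92.7% | 97.1% | 95.0% |
| 21/13 | 17.46 | 89.7% | 99.2% | 95.0% |
| 12/17 | 14.71 | 98.4% | 91.0% | 95.0% |

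With equal arms the sample size cancels from the ratio, so more participants would not help the arm means. Equal arms also make the ratio for the difference exactly 1. At 105 v 95, with SD ratios from 0.5 to 2, coverage of the difference is still 94.3-95.7%.

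**In percentage points.** Half-width for the inclisiran mean is 1.96·SD/sqrt(100).

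- 17/14: pooled 3.05, correct 3.33, so 0.3 too narrow.
- 21/13: pooled 3.42, correct 4.12, so 0.7 too narrow.
- 12/17: pooled 2.88, correct 2.35, so 0.5 too wide.

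**Check by simulating the stated ANCOVA.** At 100 v 100 with SDs 15/10, coverage was 90.0% (inclisiran), 98.6% (placebo) and 94.7% (difference), against 90.4%, 98.8% and 95.0% from the formulas. HC3 standard errors gave 95.0%, 95.0% and 94.8%.

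**Imputation.** Suppose a share p of the inclisiran arm is imputed around the control mean, 50 points away, with a within-group SD of 15. The arm's SD becomes sqrt[15² + p(1-p)·50²]. At p = 5% this is sqrt(225+118.75) = 18.5 (ratio 1.24 to 15); at 10% it is sqrt(225+225) = 21.2 (ratio 1.41). This is towards the upper end, because the SAP model conditions on the participant's own earlier values, which pull the imputed value below the control mean.

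**Subgroup differences.** The direction depends on which arm is smaller in that subgroup.

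| Inclisiran v placebo | SD 21/13 | SD 12/33 |
|---|---|---|
| 12 v 20 | 91.9% | 98.3% |
| 20 v 12 | 97.2% | 89.1% |

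Drawing each arm's subgroup count as Binomial(100, 0.16) and averaging over these draws (pooled two-sample interval, no covariate), coverage of the difference is about 95% for 21/13 and 94% for 12/33. A gap of 8 or more between arms has probability about 0.147 in either direction, but about 0.074 (1 trial in 14) in the direction that causes under-coverage.

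**The case against.** The strongest reply is that the estimand's summary measure is the difference in means (protocol 3.1), that success depends on that test alone, and that 1:1 allocation protects it. Arm means accompany that result, subgroups are supplementary, and secondary p-values are nominal. An error of 0.3-0.7 points on a reduction of about half changes no conclusion. All of this stands, and it sets the severity.

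Three stronger readings might be inferred, and the documents do not support them:

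- **That the primary test or its interval is wrong.** It is not: the SE ratio is 1 at equal arm sizes and close to 1 at 105 v 95.
- **That unstratified randomisation leaves subgroup differences generally under-covered.** Imbalance is symmetric, so under-coverage in one direction is largely offset by over-coverage in the other. What matters is unequal arm sizes within a subgroup; one subgroup being larger than another does no harm when the model is fitted separately in each. The subgroup definitions are also not in the public text, so any subgroup size is an assumption.
- **That the stated intervals definitely lack 95% coverage.** With no SDs given, this is conditional. If the spreads prove equal, there is no error.

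The reply does not remove the arm-mean point. Those intervals are promised at 95%, overall and by subgroup, and nothing in either document relaxes the pooled variance. The inclisiran-only Day 330 summary is descriptive and is not affected.

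**Conclusion.** The point holds in conditional form and is minor. If the SD of percentage change differs between arms, the arm-level intervals are miscalibrated at any sample size. Under the assumed SD pairs, coverage is about 90-93% in the noisier arm and 97-99% in the other. Which arm is affected cannot be known from the documents. Subgroup arm means share the error whatever the arm sizes; subgroup differences share it only when arm sizes within the subgroup are unequal, in a direction set by which arm is smaller. The primary superiority result stands.

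This rests on two inferences: that the unqualified ANCOVA pools variance, and that the assumed SDs are of a realistic order.

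**What to change.** In SAP 2.5.2, 2.5.6 and 2.6.6, keep the mean model and add one sentence: intervals for arm adjusted means and for subgroup differences use a residual variance per treatment group (for example PROC MIXED with a group-specific residual and Satterthwaite or Kenward-Roger degrees of freedom) or HC3 standard errors, computed in each imputed dataset before Rubin's rules. Carry the sentence to 2.6.1.1 for consistency; the full-sample differences reported there are already protected by 1:1 allocation. The primary test can stay as written.

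The cost is a few degrees of freedom and slightly wider intervals in the noisier arm. If the method were also applied to the overall difference, its half-width moved only from 4.17 to 4.20 points in simulation. With HC3 in subgroups of 12 v 24, 24 v 12 and 16 v 24, simulated coverage was 95.2-97.0% for arm means and 95.6-96.2% for differences, so slightly conservative.

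The SAP history labels Amendment 2 as prior to the final lock, which suggests that the core lock may have passed. If so, report these intervals as a labelled supplementary analysis beside the planned ones.
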